GCP	Good clinical practice
ICH	International Conference on Harmonisation
IRR	Infusion Related Reaction
LLOQ	Lower limit of quantitation
MOH	Ministry of Health
SAE	Serious Adverse Event
SOP	Standard Operating Procedures
SUSAR	Suspected Unexpected Serious Adverse Reaction
SSAR	Suspected Serious Adverse Reaction
WHO	World Health Organization

14 **Filovirus nomenclature and abbreviations used**

Disease	First subcategory	Second subcategory	Caused by
Filovirus disease	Ebola disease (ED)	Ebola virus disease (EVD)	Ebola Zaire virus (EBOV)
		Sudan virus disease (SVD)	Sudan virus (SUDV)
		Bundibugyo virus disease (BVD)	Bundibugyo virus (BDBV)
		Other specified Ebola disease	e.g. Tai Forest virus
		Ebola disease, virus unspecified	
	Marburg disease (MD)	Marburg virus disease	Marburg virus (MARV) or Ravn virus (RAVV)
		Other specified Marburg disease	
		Marburg disease, virus unspecified	

15

16

17 **1 TRIAL SYNOPSIS**

18

Type of study	Phase III adaptive platform randomised clinical trial of therapeutics
Clinical trial registration number	(pending)
Co-Sponsor(s)	World Health Organization Ministries of Health as outlined in country specific appendices
Central Coordinating Office	University of Oxford, United Kingdom

19

20 **Background:** *Filoviridae* is a family of single-stranded RNA viruses, some of which cause  
 21 severe diseases in humans. The most well-known filovirus diseases, Ebola disease and  
 22 Marburg disease, have a high mortality rate. Outbreaks are devastating to affected  
 23 communities and can have significant social and economic ramifications for affected  
 24 countries. Despite this, advancement of evidence-based treatment has been slow because  
 25 outbreaks are relatively rare, and their timing and exact location difficult to predict.

26 **Aim:** The primary aim is to identify the effect of a range of interventions on all-cause mortality  
 27 at 28 days in patients admitted to a healthcare facility with filovirus disease.

28 **Design:** This trial signifies a commitment from the World Health Organization (WHO) and  
 29 partners to prepare and pre-position a platform trial of treatments for any filovirus disease.

30 A platform trial is a clinical trial that can study multiple different interventions at the same  
 31 time and add, assess, and remove new interventions as time goes on, without having to  
 32 specify the new interventions at the start.\* Compared to a more traditional clinical trial design  
 33 (is this drug better than usual care?), a platform trial can be thought of as disease  
 34 focussed (what is the best treatment for this disease?).

35 As well as being able to add new interventions as time goes on, platform trials also have the  
 36 flexibility to update the control, or 'usual care' group as the study progresses. This is useful  
 37 for when, for example, the platform trial shows a drug it's testing to be much more effective  
 38 than 'usual care', then that drug can be used to benefit patients right away and become part  
 39 of the new 'usual care' against which all new drugs are tested in the trial, creating a potential  
 40 cycle of improvement in patient care.

41 Since some treatments might work across a variety of different filovirus diseases (e.g. host  
 42 directed therapies such as immunomodulatory drugs or drug that stabilise the vascular  
 43 endothelium) a trial that allows enrolment of patients with any type of filovirus disease would  
 44 be beneficial – a 'pan-filovirus' protocol. A pan-filovirus protocol is also favoured since it  
 45 allows a single protocol to be pre-approved and implemented for any filovirus outbreak.

---

\* See: <https://www.phctrials.ox.ac.uk/platform-trials-an-explainer>

46 The rationale for a pan-filovirus adaptive platform trial is, therefore, that:

- 47 i. A research response that depends on the design, approval, and implementation of a  
48 new clinical trial for each outbreak is usually too slow to enrol within the timeframe of  
49 a single filovirus epidemic;
- 50 ii. Enrolment across different outbreaks to a unified protocol increases the likelihood of  
51 a trial that is sufficiently powered to conclusively demonstrate a benefit or lack of  
52 benefit on mortality ;
- 53 iii. New promising interventions may emerge over time, and their efficient evaluation  
54 would benefit from an adaptive platform trial approach;
- 55 iv. Certain interventions may be applicable to more than one filovirus strain and therefore  
56 may be evaluated in a pan-filovirus protocol.

57 This protocol describes a multi-country, multi-outbreak randomised adaptive platform trial of  
58 potential treatments for filovirus disease (FVD). This includes Ebola disease, Marburg  
59 disease, and unspecified and emergent filovirus diseases. The treatment comparisons  
60 included are determined by expert consultations convened by WHO. If clear evidence of  
61 efficacy, futility, or a safety signal are not achieved for any of the comparisons during a given  
62 outbreak, the protocol permits the continuation of relevant arms of the trial in future filovirus  
63 outbreaks until a clear result is achieved.

64

[figure not shown]
65 **Protocol structure** (see figure 1 below): The trial design permits continued operations even  
66 when:

- 67 i. Promising new treatments are developed and are ready to be tested;
- 68 ii. Treatments no longer require evaluation in a trial because they have been shown to  
69 be effective or ineffective or unsafe;
- 70 iii. New countries wish to join the trial with their own regulatory requirements;
- 71 iv. Outbreaks of different filoviruses occur with different treatment options;
- 72 v. New filoviruses emerge.

73 This core protocol details the key requirements of the trial irrespective of the location or  
74 cause of an outbreak but is supplemented by appendices that describe more detailed  
75 information for an outbreak in a particular regulatory jurisdiction (Country appendices), or  
76 for a particular virus (Virus appendices). The country appendices name national  
77 investigators and partner institutions. They specifically detail adaptations to comply with  
78 local regulatory requirements. These are usually governance requirements, ethics  
79 considerations (such as proxy or minor consent processes) and changes to reporting  
80 timelines. The virus appendices provide details of the treatments to be evaluated for a  
81 particular filovirus, and any data collection additions.

82 The protocol sits alongside a detailed statistical analysis plan that will provide a pre-specified  
83 plan for assessing treatment safety and efficacy. Standard operating procedures provide  
84 site-level detail on how to interpret and implement the protocol.

85

86 **Figure 1: Protocol structure**

87

88

89 **Eligibility and randomisation:** This is a randomised controlled trial for patients receiving  
 90 inpatient care for laboratory-confirmed acute filovirus disease. In a factorial design, eligible  
 91 patients are randomly allocated (1:1) in one or more comparisons.

92

- 93 ● Monoclonal antibodies:
  - 94 ○ Targeted monoclonal antibody/cocktail\* vs no additional treatment
- 95 ● Virus-directed therapy:
  - 96 ○ Antiviral therapy\* vs no additional treatment
- 97 ● Host-directed therapy:
  - 98 ○ Host-directed therapy\* vs. no additional treatment

98

\*defined in *Virus-specific annexes*.

99 If one of the treatments is not available at the site (or is contraindicated for a given patient)  
 100 randomisation may be between fewer arms. In addition, all participants will receive usual  
 101 standard of care according to WHO guidelines, and approved treatments when they exist.

102 **Study outcomes:** The primary outcome will be 28-day mortality and the secondary outcome  
 103 will be time to viral clearance (filovirus RNA <LLOQ). Follow-up will be stopped at the earliest  
 104 of death, discharge from inpatient care, or 28 days after randomisation. Sub-group analyses  
 105 will be conducted for groups defined by the following baseline features: Filovirus strain (ED,  
 106 MD, MARV, RVV, EBOV, BDV, SUDV), age, cycle-threshold (Ct) value using quantitative

107 RT-PCR, days since symptom onset, *Filovirus* vaccination status, randomisation to other  
108 trial treatments.

109

110 **Simplicity of procedures:** To facilitate collaboration, to support treatment units seeing a  
111 large number of patients, and to minimise risks to healthcare worker safety, trial-specific  
112 procedures are streamlined and data collection is focused. Informed consent is  
113 proportionate to any additional risks involved in participation in the trial by comparison with  
114 the risks of usual care alone. Key follow-up information is recorded at a single timepoint.

115

116 **Data to be recorded:** At randomisation, information will be collected on participant age,  
117 sex, major co-morbidities, pregnancy status (in women of child-bearing age), filovirus RT-  
118 PCR time of collection and result, symptom onset date, date of admission, disease severity,  
119 any contraindications to the study treatments, filovirus vaccination status, and the name of  
120 the facility enrolling the patient. Information collected on a single follow-up form will be death  
121 (with date and probable cause), hospitalisation status (with date of discharge, if appropriate),  
122 filovirus RT-PCR Ct values, treatments provided, and renal and liver function test results. In  
123 addition to study outcomes (e.g. mortality), Adverse Events will be recorded if they fall into  
124 one of the following groups:

125

- 126 a. Adverse Events of Special Interest (AESIs; e.g. infusion-related reactions).
- 127 b. Serious Adverse Events that are not considered to be due to the underlying *Filovirus*  
128 infection.
- 129 c. Serious (per standard regulatory definition) that are considered with reasonable  
130 probability to be related to one of the study medications (i.e. Suspected Serious  
131 Adverse Reactions, which includes Suspected Unexpected Serious Reactions  
132 [SUSARs]).

133

134 Pregnancy and foetal outcomes will also be recorded.

135

136 **Numbers to be randomised:** The larger the number randomised the more accurate and  
137 informative the results will be and, over time, the more potential treatments can be assessed.  
138 In general, each comparison should be sufficiently large to provide good power (e.g. 90%  
139 power at  $2P=0.01$ ) to detect a proportional reduction in mortality of at least one third. The  
140 sample size required will be dependent on the mortality seen in patients enrolled in the trial  
141 (which will be dependent on the specific disease, and which may be lower in trial participants  
142 than the wider population hospitalised with Ebola or Marburg Disease, and which may  
143 evolve over time as treatment and supportive management evolves). The Trial Steering  
144 Committee, blind to information about the effects of ongoing treatment comparisons, will  
145 monitor blinded event rates and adjust the required sample size for each comparison as  
146 data from the trial accrue.

147 The study is co-sponsored by WHO and the Ministry of Health in each participating country.  
148 It is overseen by a Trial Steering Committee convened by the World Health Organization  
149 and a Data Monitoring Committee.

150

151 **Protocol Review:** The trial will be carried out in accordance with the Principles of the  
152 International Conference on Harmonisation Good Clinical Practice (ICH GCP) and the  
153 Principles for Good Randomised Trials developed by the Good Clinical Trials Collaborative.

154 The protocol, informed consent form(s), recruitment materials, and all participant materials  
155 will be submitted to the WHO Ethical Review Committee and, in each country where the  
156 protocol will be implemented, the relevant human research ethics and regulatory agencies.  
157 Approval of both the protocol and the consent form must be obtained before any participant  
158 is enrolled.

159 Any amendment to the protocol will require review and approval by WHO and country Ethics  
160 Review Committees before the changes are implemented to the study (unless they  
161 constitute an urgent safety measure). In addition, all changes to the consent forms will be  
162 approved by these committees.

163

DRAFT

## 164 2 BACKGROUND AND RATIONALE

### 165 2.1 Setting

166 *Filoviridae* have caused significant outbreaks in recent years, including Ebola Virus Disease  
167 in west Africa (2013-2016), Sudan Virus Disease in Uganda (2022) and Marburg Virus  
168 Disease in Equatorial Guinea and Tanzania (2023). These diseases have a high case  
169 fatality, with similarities in pathogenesis and somewhat overlapping clinical syndromes.

170 Ebola Disease is a complex multi-system illness that begins following an incubation period  
171 of 2-21 days. Illness usually begins with non-specific symptoms including fever, fatigue, and  
172 gastrointestinal distress. As the disease progresses, it is complicated by worsening  
173 gastrointestinal losses, shock, multi-organ failure, and sometimes haemorrhage. The  
174 pathogenesis of Ebola Disease is reviewed comprehensively elsewhere. The virus  
175 disseminates broadly in body tissues and increasing viral load is a predictor of severe  
176 disease and death. Severe disease is associated with coagulopathy, disruption of  
177 endothelial function and a strong inflammatory response. Estimates of the case-fatality  
178 rate are variable depending on the outbreak, but for *SUDV* infection range between 36-  
179 65%, and is usually between 50-70% for *EBOV* outbreaks.

180 Marburg Disease is less well characterised than Ebola Disease because there have been  
181 fewer cases and no large outbreaks in almost two decades. Following an incubation of 3-21  
182 days, a non-specific febrile illness develops abruptly, followed by symptoms which may  
183 include conjunctival injection, rash, and abnormal bleeding. Gastrointestinal symptoms are  
184 described, but might be less prominent than for Ebola Disease. In comparison, bleeding  
185 manifestations might be more frequent. Complications include renal and liver failure and  
186 pancreatitis. Patients die following the onset of shock and multi-organ failure.  
187 Coagulopathy, endothelial leak, and an excessive inflammatory response occur and  
188 contribute to tissue damage. As with other filoviruses, infection occurs following mucosal  
189 or broken-skin contact and the virus first infects macrophages and dendritic cells before  
190 infecting the organs. There is significant variation in case fatality rates reported for Marburg  
191 (ranging from 23-88%), with the two largest outbreaks to date with mortality above 80%.

### 192 2.2 Treatment Options

193 The association between high levels of viraemia and Filovirus Disease severity suggests  
194 that therapies that target viral replication may benefit patients, and the association with pro-  
195 inflammatory mediators and death suggests a possible role for host-directed  
196 immunomodulatory treatment.

197 This protocol allows reliable assessment of the effects of multiple different treatments on  
198 major outcomes in Filovirus Disease.

199 The treatment domains to be assessed in the protocol are:

- 200 • Monoclonal antibody/ies [specific to each virus].
- 201 • Antiviral [all patients] .

- 202       • Host-directed therapy: [all patients].

203 Further details about these treatments and the reasons for including them are provided in  
204 virus specific annexes.

205 All patients will also receive standard of care consistent with WHO guidelines, and national  
206 guidelines where these exist. This includes (but is not limited to) rehydration, analgesia and  
207 other symptom relief, nutrition, and psychosocial care. Participants might have the option  
208 to receive an experimental or licensed vaccine, and this would not interfere with their  
209 potential enrolment in this trial.

210 Where approved treatments exist, patients can receive these without interference with their  
211 potential enrolment in this trial. For *EBOV* infections, the monoclonal antibody products  
212 REGN-EB3 and mAb114 are strongly recommended by WHO and approved by the US-  
213 FDA, based on the results of a previous clinical trial, but there are no approved or  
214 recommended host-directed therapies. There are currently no approved anti-viral or host-  
215 directed treatments for *SUDV* or *MARV* or other *Filoviridae*.

### 216 **2.2.1 Modifications to the number of treatment comparisons:**

217 In this adaptive platform trial, the Trial Steering Committee (TSC) may elect to add new  
218 treatment comparisons as evidence emerges that other candidate therapeutics or supportive  
219 care strategies should be evaluated. In this situation, randomisation may be between more  
220 comparisons. Conversely, the Trial Steering Committee may decide to stop some  
221 comparisons if there is no longer important uncertainty about the effects of a treatment.

222 In some patient populations, not all trial comparisons will be appropriate (e.g. due to  
223 contraindications or other co-morbidities); in some treatment centres, not all treatments will  
224 be available (e.g. due to cold storage requirements or delays to drug production); and at  
225 some times, not all treatment comparisons will be active (e.g. due to lack of relevant  
226 approvals and contractual agreements). In any of these situations, randomisation will only  
227 be between available and suitable treatments.

### 228 **2.3 Design Considerations**

229 The trial is designed to minimise the burden on clinical staff. Eligibility criteria are therefore  
230 simple and trial processes (including paperwork) are minimised.

231 The protocol is deliberately flexible so that it is suitable for a wide range of settings, allowing:

- 232       • A broad range of patients to be enrolled in large numbers.
- 233       • Randomisation between only those treatment comparisons that are both available at  
234       the clinical service *and* not contraindicated for a given patient.
- 235       • Treatment comparisons to be added or removed according to the emerging evidence.
- 236       • Continuation of the trial across multiple outbreaks, if necessary (and where regulatory  
237       approval is in place) until a clear result is achieved.
- 238       • Additional sub-studies to be added (see section 9.7) if appropriate (but inclusion into  
239       these will not be a requirement for participation).

240 **2.3.1 Evolving standard of care**

241 Over time, effective treatments may become available and ineffective treatments and  
242 practices may be abandoned, typically as the result of reliable information from randomised  
243 human efficacy trials (including from this study). In this protocol, all patients will receive usual  
244 standard of care. Thus, randomisation will remain relevant to the current clinical situation  
245 and the incremental effects of study treatments (on top of what is usual) will be appropriately  
246 assessed.

DRAFT

## 247 3 DESIGN

### 248 3.1 Study aims

249 This is an open-label, adaptive, randomised platform clinical trial to evaluate the impact of  
250 potential treatments on mortality in patients with filovirus disease.

### 251 3.2 Eligibility

252 Patients are eligible for the study if all of the following are true:

- 253 (i) Admitted to a hospital or treatment unit for treatment of filovirus disease.
- 254 (ii) Positive filovirus RT-PCR (or neonate aged seven days or younger born to a woman  
255 with acute laboratory confirmed Filovirus Disease).
- 256 (iii) No medical history that might, in the opinion of the attending clinician, put the patient  
257 at significant risk if enrolled in the trial (e.g. known allergy to a study drug).
- 258 (iv) Not known to have been enrolled in this protocol previously.

259 In addition, if the attending clinician believes that a patient should definitely not receive one  
260 of the active drug treatments (see virus specific annexes for contraindications) or that the  
261 patient should definitely be receiving one of the active treatments (e.g. corticosteroids for a  
262 licensed indication) or they have already received a treatment in that class during their  
263 course of illness, then they will not be eligible for randomisation in that comparison. Co-  
264 enrolment in other studies and trials is not an exclusion criterion (unless there is a risk to the  
265 validity of either trial, or if co-enrolment increases risk to participants).

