### 308 3.4 Interventions

309 Details on the specific treatments included for each virus are described in virus specific  
 310 annexes.

311 **3.5 Study outcomes**

312 **3.5.1 Primary outcome**

- 313
  - All-cause mortality at 28 days following randomisation

314 **3.5.2 Secondary outcome**

- 315
  - Time (days) to *Filovirus* RNA <LLOQ (lower limit of quantitation) within 28 days

316 [Viral clearance, using results from study or routine clinical samples, is defined as

317 the first negative *Filovirus* RT-PCR test without a subsequent positive test result

318 or subsequent death. In the unlikely scenario that a patient is discharged home

319 without two successive negative RT-PCR tests, the date of the first negative test

320 or, if there is no negative test result, the date of medical discharge will be used.]

321 **3.5.3 Other outcomes**

- 322
  - Viral load (measured by cycle threshold) on blood samples taken at Day 3, 5, 7

323 and 10.

324 
  - Progression of organ dysfunction, measured on blood samples taken at Day 3, 5,

325 7, 10.

326 **3.5.4 Safety outcomes**

327 In addition to study outcomes (e.g. mortality), Adverse Events will be recorded if they fall

328 into one of the following groups:

329

- 330 a. Adverse Events of Special Interest (AESIs; e.g. infusion-related reactions).
- 331 b. Serious Adverse Events that are **not considered to be due to the underlying *Filovirus***
- 332 **infection.**
- 333 c. Serious (per standard regulatory definition) that are considered with reasonable
- 334 probability to be related to one of the study medications (i.e. Suspected Serious
- 335 Adverse Reactions, which includes Suspected Unexpected Serious Reactions
- 336 [SUSARs]).
- 337

338 Pregnancy and foetal outcomes will also be recorded.

339

340 Study outcomes will be assessed based on data recorded up to the time of death, hospital

341 discharge or 28 days after randomisation (whichever occurs first). Pregnant women will be

342 followed up to completion of pregnancy.

343

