### 351 4.1 Main analysis approach

352 For all each randomised comparison, the outcomes will be made between all participants  
353 randomised to the different treatment comparisons, irrespective of whether they received  
354 some, none, or all of their allocated treatment (i.e. these comparisons will be based on  
355 “intention-to-treat” analyses).

356 The primary analyses will involve pairwise comparisons between the active ‘experimental’  
357 and ‘reference’ arms as follows:

- 358 • Effect of monoclonal antibody: monoclonal vs. no additional treatment.
- 359 • Effect of antiviral: antiviral vs. no additional treatment.
- 360 • Effect of host-directed therapy: host-directed therapy vs no additional treatment.

361 Logistic regression adjusted for baseline levels of key prognostic factors will be used to  
362 estimate the conditional odds of 28-day mortality for each treatment group relative to its  
363 control (ie, the 28-day conditional odds ratio) and its 95% confidence interval. A two-tailed  
364 P-value <0.05 will be considered as statistically significant. Logistic regression (based on  
365 vital status at Day 28, regardless of the time to death within this 28-day range) will be used  
366 in preference to Cox regression because the latter might give undue weight to the exact  
367 times of death of the very poor-prognosis patients (thereby giving inadequate weight to the  
368 death or survival of the better-prognosis patients). However, for illustrative purposes,  
369 Kaplan-Meier plots showing the pattern of survival over the first 28 days will also be created,  
370 both overall and within prognostic categories. For the primary objective of assessing the  
371 effects of each study treatment on 28-day mortality, discharge alive before day 28 will be  
372 assumed as survival to day 28 (unless there are additional data confirming otherwise).

373 For the secondary objective of assessing the effects of each treatment on time to filovirus  
374 RNA <LLOQ within 28 days, differences in median days to filovirus RNA <LLOQ will be  
375 tested using the Wilcoxon rank-sum test, imputing deaths prior to day 28 as the worst ranks,  
376 with earlier deaths having a worse rank than later deaths. The study will collect viremia data  
377 at baseline and approximately days 3, 5, 7, 10. Patients who are discharged from inpatient  
378 care but without an available *Filovirus* RT-PCR test result will be assumed to have *Filovirus*  

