### 526 6.2 Identification

527 Potential participants will be identified from the point that the treating clinician in a  
528 participating clinical site is notified of a positive *Filovirus* RT-PCR result by the laboratory.  
529 Patients are eligible for enrolment at any point during their acute illness.

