### 530 6.3 Consent

531 Informed consent must be obtained for each patient before enrolment into the study. To  
532 maximise the opportunity for potential participants to make their own decisions about  
533 participation prior to potential clinical deterioration, patients with suspected Filovirus Disease  
534 can be approached for consent, although they will not be enrolled in the study until laboratory  
535 confirmation of disease.

536 For children, consent will be sought from their parents or legal guardian. The age where a  
537 child is able to consent for themselves will adhere to legislation in the country of trial  
538 operation (provided in country-specific annexes). Where possible, children who are 10 years  
539 old or more will also be asked for assent.

540 If an adult patient cannot provide consent, reasonable attempts will be made to reach the  
541 next of kin to provide consent by proxy.

542 Proxy consent must be witnessed but may be obtained over the telephone if a  
543 parent/guardian or legally acceptable representative cannot be physically present (e.g. due  
544 to treatment unit visiting rules or parental quarantine, isolation, or illness).

545 Due to the severity of Filovirus Disease, patients who lack capacity to consent due to severe  
546 disease, and for whom a relative to act as the legally designated representative is not  
547 available, randomisation and consequent treatment will proceed with consent provided by a  
548 clinician (independent of the clinician seeking to enrol the patient and not connected with  
549 the conduct of the trial) who will act as the legally designated representative (if allowed by  
550 local regulations). If a participant subsequently regains capacity prior to discharge, they  
551 should be provided with information about the trial, their rights, and how to exercise them.  
552 Provision of such information should be documented in the medical record.

553 Consent will include provision for secondary use of data which includes use by the  
554 pharmaceutical partners that supply study treatments, regulators, public health and  
555 academic organisations.

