#### 556 **6.4 Baseline information**

557 The following information will be recorded. For laboratory tests, the most recent value  
558 obtained for routine clinical practice is used, if available.

- 559 ● Clinical facility (e.g. name of treatment unit) enrolling patient.
- 560 ● Patient details (e.g. name, date of birth, sex).
- 561 ● Major comorbidities (e.g. malaria, HIV, tuberculosis, diabetes, malnutrition, previous  
562 *Filovirus* infection).
- 563 ● Date of *Filovirus* Disease symptom onset.
- 564 ● Date of admission to treatment facility.
- 565 ● Latest *Filovirus* test result (date, strain, Ct value).
- 566 ● Vital signs.
- 567 ● Focused symptom assessment (bleeding, confusion).
- 568 ● Biochemistry results (creatinine, ALT and/or AST).
- 569 ● Malaria test result.
- 570 ● Pregnancy test result (in women with childbearing potential) with estimated gestational  
571 age or trimester.
- 572 ● Contraindication to [each](#) of the study drugs.
- 573 ● Use of relevant concomitant medication (e.g. antivirals, corticosteroids, antimalarials).
- 574 ● Vaccination (including date) for *Filovirus*.

575

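### The viral-clearance comparison takes in participants with no virus shown at randomisation, which dilutes this secondary analysis but leaves type I error and 28-day mortality untouched

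*Protocol*

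**What the plan says.** **Who enters.** Protocol 3.2 criterion (ii) requires "Positive filovirus RT-PCR (or neonate aged seven days or younger born to a woman" with laboratory-confirmed disease. The neonate qualifies on the mother's diagnosis. For other patients, the criterion does not say how recent the positive result must be. Section 6.2 adds: "Patients are eligible for enrolment at any point during their acute illness". Section 6.4 records "Latest *Filovirus* test result (date, strain, Ct value") at baseline, that is, the latest available result rather than a test on the day of randomisation.

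**How the synopsis and consent section describe them.** The synopsis describes the trial as one for patients receiving "inpatient care for laboratory-confirmed acute filovirus disease". Section 6.3 says of patients with suspected disease that they "can be approached for consent, although they will not be enrolled in the study until laboratory" confirmation. Neither mentions the neonate exception.

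**How clearance is scored and compared.** Section 3.5.2 takes the first negative RT-PCR "test without a subsequent positive test result" or later death. It asks for no positive test at or near randomisation. Section 4.1 sets the population: "For all each randomised comparison, the outcomes will be made between all participants" randomised, by intention to treat. The test is a Wilcoxon rank-sum with deaths before day 28 given the worst ranks, earlier deaths being worse. A participant discharged without an RT-PCR result is taken as below the limit of quantitation on the day of discharge.

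**The concern.** Read together, 3.2, 3.5.2 and 4.1 put into a time-to-clearance comparison some participants in whom there may be nothing to clear. Neonates enrolled on the mother's diagnosis are one such group. Because criterion (ii) sets no recency, patients whose latest RT-PCR before randomisation is already negative may be another. For that second group 3.5.2 does not even say where the clock stands: the first negative test precedes randomisation, so the time is zero or negative unless a later test is used.

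A survivor in either group with an early negative test is ranked among the fastest clearances in both arms, and that rank carries no information about treatment. Such ranks pull the comparison towards no difference. What is at stake is the sensitivity of the only secondary outcome and the size of its estimated effect.

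**Working it through.** **1. The plan's own figures.** These concern mortality only; no power is claimed for viral clearance. At 260 per arm (520 in total, section 4.2), 50% v 33.3% gives 90.3% power at 2P=0.01, and 50% v 37.5% gives 82.1% at 2P=0.05. Both agree with the stated more than 90% and more than 80%. The present point does not touch them.

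**2. How a participant with no virus shown at entry is scored.**
- Survives, negative test at or near baseline: among the best ranks.
- Survives, first tested at about day 3: tied with genuine early clearers.
- Discharged with no result: the discharge day.
- Dies before day 28: a worst rank.

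Only the first two produce early clearances.

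**3. Expected dilution.** Let f be the share in each arm scored best regardless of allocation, and let δ be the rank effect (the probability that a treated participant does better than a control, counting ties as half, minus 0.5) among the rest. Take a random treated-control pair:
- Both members are informative with probability (1-f)², and contribute δ.
- Pairs with one uninformative member cancel between the arms.
- Pairs with two uninformative members tie.

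The effect becomes (1-f)²δ with nearly unchanged variance.

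**4. Simulation.** From the protocol: 1:1 allocation, 260 per arm, 50% control mortality, Wilcoxon with deaths worst. Assumed: gamma clearance times read off a sampling grid, median 10 days in controls; two-sided 0.05 for this test; f; and that all of f survive and score day 0, the least favourable scoring. 4,000 runs per cell, so the simulation error is at most √(0.25/4000) = 0.8 points.

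| Power at f = | 0 | 1% | 2% | 5% | 10% | 20% |
|---|---|---|---|---|---|---|
| (a) deaths 50% to 37.5%, median 10 to 8 days | 0.976 | 0.965 | 0.968 | 0.940 | 0.885 | 0.717 |
| (b) deaths 50% to 37.5%, no clearance effect | 0.699 | 0.679 | 0.666 | 0.611 | 0.521 | 0.360 |
| (c) deaths equal at 50%, median 10 to 7 days | 0.428 | 0.423 | 0.410 | 0.350 | 0.318 | 0.202 |

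The rank effect follows the formula. In (a), δ = 0.099 at f=0. At 10%, 0.099 × 0.81 = 0.080 (simulated 0.080). At 20%, 0.099 × 0.64 = 0.063 (simulated 0.064).

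Loss against f=0: about 0-3 points at 1-2%, 4-9 at 5%, 9-18 at 10% and 23-34 at 20%. With no treatment effect the rejection rate was 0.05-0.06 at every f, with no trend.

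**5. How much the fix recovers.** Not all of that loss, because restriction also removes participants. Relative to f=0 at full size, z is multiplied by (1-f)² if they are kept and by (1-f)^0.5 if they are left out. Write d = 1.96 + Φ⁻¹(power at f=0), which is 3.94, 2.48 and 1.78 for (a), (b) and (c). Worked for (b) at f=10%:
- Kept: 2.48 × 0.81 = 2.01, power Φ(0.05) = 0.52.
- Left out: 2.48 × 0.949 = 2.35, power Φ(0.39) = 0.65.

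Across the three scenarios the recovery is about 1-3 points at f=2%, 3-7 at 5% and 7-13 at 10%.

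**The case against.** **Neonates will be few.** Section 3.2.1 says foetal survival is rare in Ebola Disease, and it counts three known Marburg pregnancies with one neonate delivered, who died. A neonate must also meet criterion (i), admission for treatment of filovirus disease. This stands: if only neonates contribute, the loss is probably at the bottom of the range.

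**Already-negative patients are nowhere described.** A reader might infer that the protocol plans to enrol them. It does not. Everyone but the neonate needs a positive RT-PCR, section 6.2 starts identification when the site "participating clinical site is notified of a positive *Filovirus* RT-PCR result by the laboratory", and entry is confined to acute illness. Virus was once shown in these patients. All that can be said is that their enrolment is not ruled out.

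**They do not all take the best ranks.** A reader might infer that they do, whatever happens. Section 4.1 ranks deaths worst and assigns untested discharges the discharge day, so the simulation's scoring is the severe case.

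**There is no bias towards a false positive.** A reader might also infer an inflated error rate. The ranks concerned are the same in both arms, and the null results do not support that.

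**The statistical analysis plan could deal with it.** Coding of a negative or missing Ct value belongs there and is not pressed here. The clearance definition and the all-randomised population, however, are fixed in this protocol, so a later restriction would change what it states.

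**The contradiction is thin.** Section 6.3 is about approaching suspected cases and does not say that every participant is laboratory-confirmed; the synopsis is a summary. This stands in part: 3.2 is explicit, so what remains is a wording mismatch.

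**Conclusion.** The point holds as a limited one. The protocol's own definitions place participants with no virus shown at randomisation in the clearance comparison, and those who survive with an early negative test are scored as early clearances irrespective of allocation. The consequence is a smaller estimated effect and lower power for the secondary outcome: about 0-3 points if 1-2% are affected, 4-9 at 5% and 9-18 at 10%. Part of that is recovered by restricting the comparison. It becomes material only from roughly 5-10% upwards.

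These sizes rest on an assumed share, on assumed clearance times and on the severe scoring described above. The documents give no share. The primary outcome and the sample size of about 520 are unaffected.

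**What to change.** In 3.5.2 and 4.1, state that time to viral clearance is compared among participants whose most recent RT-PCR before randomisation was positive, with all randomised participants as a sensitivity analysis. That status is fixed before allocation, so the comparison remains randomised, and 6.4 already records the result and its date.

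Leave criterion (ii) unchanged. Requiring the latest test to be positive for entry would remove patients from the mortality analysis for the sake of a secondary outcome. Keep every randomised participant in the mortality analysis.

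Reconcile the synopsis and 6.3 with 3.2 by naming the neonate exception in both.

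The cost is a few sentences and slightly fewer participants in the secondary analysis.
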